5.2.2.1. Special Circumstances for Informed Consent

This clinical investigation excludes individuals unable to make the decision to participate in a clinical investigation on their own or who are unable to fully understand all aspects of the investigation that are relevant to the decision to participate, or who could be manipulated or unduly influenced as a result of a compromised position, expectation of benefits or fear of retaliatory response. This clinical investigation excludes individuals under the age of 18 or age of legal consent from the clinical investigation population. The clinical investigation excludes Individuals unable to read or write. The clinical investigation excludes pregnant or breastfeeding women.

Clinical Investigation Plan

5.3. Eligibility Criteria

5.3.1. General Eligibility Criteria

Assessment for general eligibility criteria is based on medical records of the site and interview with a candidate patient. Patients must meet all inclusion criteria to participate in the clinical investigation. If any exclusion criteria are met, the patient is excluded from the clinical investigation and cannot be enrolled (screen failure).

If any clinical and/or laboratory tests are required for patient screening and are not included in a site's standard tests, they must be completed after written informed consent is obtained.

5.3.2. Inclusion Criteria

1. Subject is indicated for an SCS system, or has an implanted SCS system and is scheduled to receive an IPG replacement.
2. Subject is scheduled to receive a new IPG permanent implant and has completed a successful SCS trial in the last 6-months, OR subject is scheduled to undergo an all-in-one procedure OR has an implanted SCS system for an approved chronic pain indication.
3. Subject has a documented NRS pain score of ≥ 6 after at least 5 days without stimulation OR has an implanted functioning SCS system with NRS pain score of ≤ 4 .
4. Subject must provide written informed consent prior to any clinical investigation-related procedure.
5. Subject is at least 18 years at the time of enrollment.
6. Subject is capable and willing to recharge an implanted IPG.

5.3.3. Exclusion Criteria

1. Subject's SCS trial was unsuccessful.
2. Subject is currently participating, or intends to participate, in another clinical investigation that may confound the results of this study, as determined by Abbott.
3. Subject has or will receive more than one IPG.
4. Subject is pregnant or breastfeeding or plans to become pregnant during the clinical investigation follow-up period.
5. Subject has other anatomic or comorbid conditions, or other medical, social, or psychological conditions that, in the investigator's assessment, could limit the subject's ability to participate in the clinical investigation.
6. Subject has or is scheduled to receive an intrathecal pump.
7. Subject is part of a vulnerable population (section 5.2.2 of the clinical investigational plan).

5.4. Subject Enrollment

A subject is considered enrolled in the study when the following conditions are met:

1. Subject has provided written informed consent, and
2. Subject has been determined to meet all inclusion/exclusion criteria.

Clinical Investigation Plan

5.5. Subject Withdrawal and Discontinuation

Each subject meeting all eligibility criteria shall remain in the clinical investigation until completion of the required follow-up period; however, a subject's participation in any clinical investigation is voluntary. The subject has the right to withdraw at any time without penalty or loss of benefit. Conceivable reasons for discontinuation may include the following:

- Subject does not have the Gemini neurostimulation system implanted within 60 days of enrollment
- Subject death
- Subject voluntary withdrawal
- Subject is lost to follow-up as described below
- Subject's follow-up is terminated according to Section 3.3
- Subject's Gemini rechargeable SCS system has been explanted
- Subject's trial was unsuccessful (for 'all-in-one' procedures)

Sites must notify the Sponsor of the reason for subject discontinuation. Investigators must also report this to their respective EC as defined by their institution's procedures.

No additional follow-up is required or data recorded from subjects once withdrawn from the clinical investigation.

However, if a subject withdraws from the investigation due to problems related to the safety or performance of the device under investigation, the investigator shall ask for the subject's permission to follow the subject's condition outside of the clinical investigation.

Lost to Follow-up

If the subject misses the scheduled 6-week follow-up visit and the attempts at contacting the subject detailed below are unsuccessful, then the subject is considered lost to follow-up. Site personnel shall make all reasonable efforts to locate and communicate with the subject (and document these efforts in the source documents), including the following:

- A minimum of two telephone calls or electronic communications on different days over the specified follow-up window to contact the subject should be recorded in the source documentation, including date, time and initials of site personnel trying to make contact.
- If these attempts are unsuccessful, the site should send a letter (certified if applicable) to the subject.

Note: Telephone contact with a General Practitioner, another physician or a relative without the presence of the subject, as well as indirect documentation obtained via discharge letters, will not be considered as subject contact.

Clinical Investigation Plan

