3.1. Clinical Investigation Procedures and Follow-up Schedule

The flowchart and the follow-up requirements of this clinical investigation are described below. Enrollment, baseline and permanent implant can occur on the same day.

Clinical Investigation Plan

Figure 1: Clinical Investigation Flowchart

Clinical Investigation Plan

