5.7. Total Expected Duration of the Clinical Investigation

Subjects participating in this clinical investigation will be followed for approximately 6 weeks after the permanent implant procedure. [REDACTED]

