6.3. Follow-up Assessments

6.3.1. 2-Week Follow-up (In-Person, Phone Call or Telehealth Visit)

A 2-week follow-up visit, which may occur in person, by telephone or as a telehealth visit, will occur 10-14 days after permanent implant. The 2-week follow-up visit provides an opportunity for the site to confirm that the patient understands the charging plan and has the opportunity to report any adverse events. If the clinician programmer is connected to the subject's IPG all reports will be downloaded. The following data will be collected:

- All serious adverse events including deaths (if applicable)
- Non-serious adverse events related to device/procedure/stimulation/charging/MRI (if applicable)
- Charging history (if applicable)
- Stimulation programs used since permanent implant (if applicable)
- Stimulation programs available at the end of the visit (if applicable)
- Withdrawal (if applicable)
- Device Deficiency (if applicable)
- Additional Surgery (if applicable)

6.3.2. 6-Week Follow-up (In-Person Visit)

Subjects will be followed at a 6-week follow-up visit that will occur 30-45 days after permanent implant. The following data will be collected:

- All serious adverse events including deaths (if applicable)
- Non-serious adverse events related to device, procedure, stimulation, charging, or MRI (if applicable)

Clinical Investigation Plan

- NRS
- PROMIS-29
- Patient satisfaction
- Patient charging experience
- Charging history
- Stimulation programs used since permanent implant
- Stimulation programs available at the end of the visit
- Withdrawal (if applicable)
- Device Deficiency (if applicable)
- Additional Surgery (if applicable)

During the 6-week follow-up visit, site personnel will connect to the subject's IPG using the CP. Site personnel will use the CP to collect the charging history, programming and program use details as PDF files.

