7.3. Adverse Event and Device Deficiency/Device Malfunction Reporting

7.3.1. Adverse Event Reporting

Safety surveillance and reporting starts as soon as the patient completes the ICF. All serious adverse events and any device-related adverse events, including those observed during the implant procedures and all-in-one/ on-table trials, will be reported.

Safety surveillance and reporting will continue until the subject performs the last follow-up visit, the subject is deceased, the subject concludes participation in the clinical investigation, or the subject withdraws from the clinical investigation. All serious and non-serious procedure- and device-related adverse event data, including deaths and device deficiency data, will be collected throughout the life of the study and will be reported to the Sponsor on a CRF. Additional information with regards to a procedure- and device-related adverse event should be updated within the appropriate CRF.

Unchanged, chronic, non-worsening or pre-existing conditions are not AEs and should not be reported.

The Sponsor will provide an offline form to allow the investigator to report SAEs in the event the entry cannot be made in the EDC. This does not replace the EDC reporting system. Sites must still enter all information in the EDC system as soon as feasible.

SAE Reporting

The investigator must report all SAEs to the Sponsor as soon as possible but no later than outlined below.

Clinical Site	Reporting timelines
All Sites	Sites must report SAEs to the Sponsor no later than 3 calendar days from the day the site personnel became aware of the event or as per

Clinical Investigation Plan

	the investigative site’s local requirements, if the requirement is more stringent than those outlined.
--	--

Sites must record the date the site staff became aware that the event met the criteria of an SAE in the source document. The Investigator will further report the SAE to the local EC according to the institution’s EC reporting requirements.

The following adverse events will be collected in this study for investigational devices as well as the approved devices:

- All serious adverse events including deaths
- Non-serious adverse events related to device/procedure/stimulation/Charging/MRI
- USADE
- DD

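### After a failed all-in-one trial, the legible protocol schedules no safety contact, so a lead-surgery SAE that appears after discontinuation may go unrecorded in the descriptive all-SAE endpoint

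*Protocol*

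**What the plan says.** Inclusion criterion 2 (protocol section 5.3.2) admits subjects scheduled for an all-in-one procedure, so the trial result is not known when they consent. Section 5.5 gives as one conceivable reason for discontinuation: "Subject's trial was unsuccessful (for 'all-in-one' procedures". The same section adds: "No additional follow-up is required or data recorded from subjects once withdrawn from the clinical investigation". Its one provision for the time after withdrawal applies "if a subject withdraws from the investigation due to problems related to the safety or performance of the device under investigation"; it depends on the subject's permission and places the follow-up outside the investigation.

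Section 7.3.1 starts safety surveillance at consent. It covers SAEs and device-related events, "including those observed during the implant procedures and all-in-one/ on-table trials, will be reported". Surveillance runs to the last visit or death, or until "the subject concludes participation in the clinical investigation, or the subject withdraws from the clinical investigation".

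Follow-up is anchored to implantation. Section 5.7 says: "Subjects participating in this clinical investigation will be followed for approximately 6 weeks after the permanent implant procedure". The 2-week visit (section 6.3.1) "will occur 10-14 days after permanent implant", and the 6-week visit (section 6.3.2) falls on days 30 to 45 counted from the same date. The schedule of events in section 6.3.5 uses the same two windows.

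Section 4.2 makes all SAEs an additional endpoint, reported descriptively. Section 8.6 keeps SAEs from subjects who withdraw before the IPG implant.

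**The concern.** The plan wants SAEs in these subjects to count, but in the legible text it has no planned means of learning about those that surface after the subject has left. The subject has had a lead placed in the epidural space. The risks listed in section 15.2 include infection, epidural hemorrhage and CSF leakage, and such events need not show themselves on the operating table.

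At stake is the completeness of the all-SAE table. A reader of the final report would take it to cover everyone who underwent study-period surgery, while for this group it could be silent about the time after discontinuation.

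**Working it through.** There is no plan figure to reproduce; the question is settled by setting the provisions side by side. The documents do not define the all-in-one procedure. I read it, from the pairing with on-table trials in section 7.3.1, as lead placement and test stimulation in the same session as the intended IPG implant.

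1. **Can such a subject be in the study?** Yes. Section 5.3.2 admits them, and section 5.5 treats a failed trial as a discontinuation. There is some tension with section 5.4 and exclusion criterion 1, under which an unsuccessful trial rules a subject out. Surveillance begins at consent either way, so the point does not depend on this.
2. **When does observation end?** At withdrawal or conclusion of participation (sections 5.5 and 7.3.1). No legible text sets a date or a minimum for a failed all-in-one trial. Early exit is allowed, not required.
3. **Is there a scheduled contact before or after that?** Scheduled safety contacts after the procedure: 2 for an implanted subject (2-week and 6-week); 0 for a subject without an IPG, because both are counted from implantation. Unscheduled visits (section 6.3.4) are defined as falling between the required visits, so they do not create a contact either.
4. **Does the provision after withdrawal help?** Not normally. It concerns problems with the device under investigation. The leads are on-market products (section 2.2.1), and a failed trial is not in itself such a problem. Data gathered under it would also lie outside the study.
5. **Does the plan mean to keep these SAEs?** Yes. Section 4.2 covers all SAEs, section 7.3.1 collects events for approved as well as investigational devices, and section 8.6 keeps SAEs whichever of its two sentences applies to a failed on-table trial.
6. **What is captured anyway?** Events during the on-table trial and up to discontinuation (section 7.3.1). Section 11.3 also requires source notes on the subject's condition at withdrawal.
7. **Does it reach the confirmatory endpoint?** No. That endpoint counts SAEs adjudicated as related to the IPG and/or charging system (section 4.1). Under SAP section 2.3.1 a subject is evaluable by completing the 6-week visit or by having such an SAE before earlier termination. A subject without an IPG has no exposure to the implanted, charged device.

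What remains is one class of event: a lead-surgery SAE first appearing after discontinuation in a subject who received no IPG.

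**The case against.** The strongest objection is that the missing rule may exist where we cannot see it. Section 3.1 says "The flowchart and the follow-up requirements of this clinical investigation are described below", and the flowchart is the natural place for a failed-trial branch. Text is also redacted in sections 5.6, 5.7 and 8.1 and in SAP section 2.1. This stands as a limit: the point can be made only about the legible text.

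Second, section 7.3.1 says that procedure- and device-related event data, deaths included, are collected for as long as the study runs, and section 5.5 opens with the default that eligible subjects stay until required follow-up is complete. These show the intent, but neither clearly overrides the explicit stop at withdrawal, and the required follow-up is undefined for someone never implanted. The 60-day limit from enrollment to implant is a deadline, not an observation period.

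Third, the stop rule is general: an implanted subject who withdraws early also has no minimum. That is fair. The difference is that an implanted subject has visits scheduled unless something intervenes, whereas a failed-trial subject has none by design.

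Fourth, the study is about the new charging system (section 1.1.2) and the leads are on-market, so ending follow-up in subjects never exposed to the investigational IPG is a defensible choice. This is largely right and sets the priority.

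A reader might go further and infer that adverse events of failed trials are discarded, that section 8.6 is contradicted, or that patients are left without care. The documents support none of these. Events up to exit are reported, section 8.6 governs only the analysis of what was recorded, and nothing says that clinical aftercare stops.

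**Conclusion.** The point holds as a small gap in data capture. In the legible text, a subject who had a lead placed but received no IPG has no scheduled safety contact after the procedure, and a later lead-surgery SAE need not be recorded. The consequence is confined to the descriptive all-SAE endpoint.

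No probability of a missed event can be given. The documents state neither how many all-in-one trials may fail nor how often or when lead-surgery SAEs occur, and the safety population is redacted. If no such trial fails, nothing is lost. A reader might infer that the confirmatory safety rate is understated; it is not, because it concerns IPG- and charging-related events.

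The conclusion rests on three assumptions: that no rule sits in the missing figures or redactions, that an all-in-one procedure involves lead placement before the trial result is known, and that a site uses the early exit that section 5.5 allows. It is an improvement to consider, at low priority.

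**What to change.** In protocol sections 5.5 and 7.3.1, state that a subject who had a lead placed in an all-in-one procedure but received no IPG stays under adverse event surveillance until one telephone contact, unless the subject withdraws voluntarily. The preferred timing is 30-45 days after the procedure, which matches the window for implanted subjects. A call at 10-14 days, which borrows the remote format of the 2-week visit, is the minimum, but it would leave later events unseen.

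Report SAEs in these subjects separately, with their number as the denominator. In SAP section 3.2, list a failed on-table trial as its own early-termination reason; the reasons now named there do not include it, so the count is not assured. Saying in protocol section 8.6 which sentence covers a failed on-table trial would be an optional clarification.

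The cost is one sentence in each of the two protocol sections, a line or two in the SAP, and one call per failed trial. The confirmatory denominator does not change.

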6.3.5. Schedule of Events

Clinical Investigation Plan

CIP Activity	Enrollment	Baseline	Permanent Implant Procedure	Follow-up visits 2-week (10-14 days post implant)	Follow-up visits 6-week (30-45 days post implant)	Unscheduled visit
Subject evaluated for eligibility	X					
Informed Consent Process	X					
Demographics		X				
Medical History		X				
Pain diagnosis and pain location		X				
NRS for pain intensity		X			X	
PROMIS-29		X			X	
Patient charging experience					X	
Patient Satisfaction					X	
Implant procedure and system data			X			
Device Programming			X	(X)	X	(X)
Charging History				(X)	X	(X)
Stimulation programs used				(X)	X	(X)
Stimulation programs available			X	(X)	X	(X)
Device deficiency			(X)	(X)	(X)	(X)
Additional surgery (System revision, Replacement/Explant)				(X)	(X)	(X)
Serious adverse events		(X)	(X)	(X)	(X)	(X)
Procedure- Device-charger- stimulation- MRI-related Adverse Events			(X)	(X)	(X)	(X)
Withdrawal		(X)	(X)	(X)	(X)	(X)

(X)-Indicates event may occur at visit

Clinical Investigation Plan

7. Adverse Events

To comply with worldwide standards and guidelines on clinical investigation adverse event reporting, the Sponsor has adopted uniform and worldwide applicable standard definitions and reporting timelines to be used and adhered to by the investigators.

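### A first IPG- or charging-related SAE after early withdrawal cannot enter the confirmatory rate, and event-free leavers drop out of its denominator

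*Protocol*

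**What the plan says.** The confirmatory endpoint is reported per subject: the number and percentage with an SAE related to the IPG or charging system, with an exact Clopper-Pearson 95% interval (Protocol 8.2.1, SAP 2.3.1). Protocol 4.1 plans no hypothesis test but uses the endpoint data to confirm that the system works as intended.

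On withdrawal, Protocol 5.5 states: "No additional follow-up is required or data recorded from subjects once withdrawn from the clinical investigation". For subjects who leave because of device safety or performance problems it adds that "the investigator shall ask for the subject's permission to follow the subject's condition outside of the clinical investigation". Protocol 7.3.1 begins "Safety surveillance and reporting will continue until the subject performs the last follow-up visit" and goes on to list withdrawal among the points at which surveillance ends.

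The time point itself is set in Protocol 6.3.2: "Subjects will be followed at a 6-week follow-up visit that will occur 30-45 days after permanent implant".

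SAP 2.3.1 takes the safety population and restricts the evaluable subjects to two groups: those who complete the 6-week visit, and those who left earlier but had a related SAE no later than their exit. A parallel definition applies to charging-system SAEs alone. SAP 2.7 uses available data and imputes nothing. Protocol 8.6 reads differently: a subject who leaves once the implant procedure is under way stays in the endpoint analysis with whatever data exist.

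**The concern.** Subjects who leave over a device safety or performance problem are plausibly the ones most closely linked to the endpoint, and Protocol 5.5 foresees them. Protocol 1.1.2 says the study is meant to pick up serious effects of the new component. Yet for these subjects recording stops at exit, and the follow-up that may continue has no visible route to the study CRFs, the Clinical Events Committee (CEC) or the endpoint.

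Whether a leaver counts also depends on the outcome: with a related SAE by exit the subject is in the denominator, without one the subject is out. The Protocol and SAP disagree on this, and the choice should be made before data are seen. With about 20 evaluable subjects, one event is the difference between a reported rate of zero and a rate above zero.

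**Working it through.** **What is lost and what is not**, from the passages read together:

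- A related SAE at or before exit, including one that prompts the withdrawal, is counted.
- A further event in a subject already counted changes nothing, because the rate is per subject.
- A first related SAE after exit and before the 6-week time point, including an earlier problem that only then becomes serious, is not recorded (Protocol 5.5, 7.3.1) and its subject is not evaluable (SAP 2.3.1).
- An event-free leaver is not evaluable under SAP 2.3.1 but is included under Protocol 8.6.

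**Inputs.** The target is 20 implanted subjects who complete follow-up (Protocol 5.6). The interval is exact two-sided 95% Clopper-Pearson. The derivation of 20 is redacted, so there is no calculation of the plan's own to reproduce. The visible text gives no withdrawal rate, and an allowance may be redacted. The number of leavers below is therefore an assumption.

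**Formulas.** For x events in n subjects, the lower limit is the 0.025 quantile of Beta(x, n − x + 1) and the upper limit the 0.975 quantile of Beta(x + 1, n − x). For x = 0 the lower limit is 0 and the upper limit is 1 − 0.025^(1/n).

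- 0/20: 1 − 0.025^(1/20) = 16.8%
- 0/21: 1 − 0.025^(1/21) = 16.1%
- 1/21 = 4.8%: lower limit 1 − 0.975^(1/21) = 0.1%; upper limit, the 0.975 quantile of Beta(2, 20), = 23.8%

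**Twenty completers and one assumed leaver with no event by exit:**

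| Situation | SAP 2.3.1 | Protocol 8.6, available data | Status known to the 6-week time point |
|---|---|---|---|
| No event in completers; leaver has a later related SAE | 0/20 (0 to 16.8%) | 0/21 (0 to 16.1%) | 1/21 = 4.8% (0.1 to 23.8%) |
| No event in anyone | 0/20 (0 to 16.8%) | 0/21 (0 to 16.1%) | 0/21 (0 to 16.1%) |
| One event in completers; leaver event-free | 1/20 = 5.0% (0.1 to 24.9%) | 1/21 = 4.8% (0.1 to 23.8%) | 1/21 = 4.8% (0.1 to 23.8%) |

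The first row shows the rate understated by a lost event. The third shows it overstated by a lost event-free subject. The first row also shows that aligning the denominator with Protocol 8.6 does not recover the event. It counts the leaver as event-free, so the data collection has to change as well.

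**The case against.** The strongest reply is that this is a small descriptive study with no test and no visible threshold, that any SAE prompting an exit is already counted, and that the remaining gap is narrow and vanishes if nobody leaves early. All of that stands. It limits the size of the point but does not remove it, because no definition of the redacted populations can supply events that Protocol 5.5 and 7.3.1 say are not recorded.

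A second reply is that the adverse-event summary in SAP section 3 (around headings 3.1 and 3.2) already reports SAEs by relatedness on the safety population, without the evaluable restriction. This largely stands: event-free leavers in that population are not dropped from every SAE percentage. Two limits remain. SAP 1.4.2 describes the additional SAE endpoint as SAEs other than the confirmatory one, and that summary cannot contain unrecorded events either.

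A third reply is that Protocol 8.6 speaks of endpoints in general and leaves detail to the SAP. That is a fair reading, but the two texts still give different denominators for the same endpoint.

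A reader might also infer that the explant passages contradict each other, since Protocol 5.5 lists "Subject's Gemini rechargeable SCS system has been explanted" while the schedule in 6.3.5 has a follow-up row for revision, replacement or explant. The documents do not support that. Protocol 5.5 introduces its list with "Conceivable reasons for discontinuation may include the following", and a bracketed X in the schedule means only that an event may happen at that visit; withdrawal is marked the same way. What remains is an ambiguity about whether explant ends SAE recording.

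**Conclusion.** The point holds, at moderate weight. As written, the rules exclude a first related SAE after exit from the confirmatory rate and make the denominator depend on the outcome, in disagreement with Protocol 8.6.

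A reader might infer that the plan hides harm. The documents do not support a direction. Lost events lower the rate, while dropping event-free leavers raises it if any event occurs and widens the interval, so the net effect is unknown.

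With one assumed leaver, the reported result is 0/20 where the full count would be 1/21 or 0/21. The intervals overlap widely, and no formal decision visible in the documents would change. The conclusion rests on the visible evaluable clause in SAP 2.3.1, since the population definitions are redacted, and its size rests on at least one subject leaving early.

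**What to change.** These are changes to data collection and reporting only.

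1. **Protocol 5.5 and 7.3.1.** For subjects in whom the implant procedure has begun, who discontinue early and who give permission, continue to record SAEs on study CRFs and send them to the CEC until one safety contact 30-45 days after implant. Say that this contact does not make the subject a completer of the 6-week visit. State whether explant ends SAE data collection.
2. **SAP 2.3.1, both evaluable definitions.** Keep the safety population as the base and retain every subject counted now. Add subjects whose SAE status is known through that contact, with or without an event. Do not replace the safety population with implanted subjects: its definition is redacted, and the change could drop an event from an implant begun but not completed.
3. **SAP 2.3.1 and Protocol 8.6.** Also report the confirmatory rate over the full safety population for available data. Present it beside the evaluable rate, because it treats unknown status after exit as event-free. The SAE summary in SAP section 3 already uses this population, so the extra work is small. List non-evaluable subjects with exit reason and date of last SAE contact.

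The cost is a Protocol and SAP amendment with ethics committee handling, possibly consent wording, and about one contact per leaver. No extra patients are needed. Subjects who refuse or are lost to follow-up stay unknown and should be shown as such.
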